
USDHHS (2016). E-cigarette Use Among Youth and Young Adults: A Report of the Surgeon General. Atlanta, GA: USDHHS, CDC, National Center for Chronic Disease Prevention and Health Promotion, Office on Smoking and Health.

2. * Describe the study hypothesis and/or research questions. Use lay language whenever possible.

The purpose of this study is to determine if abuse liability indices will be impacted by varying flavors and ECIG nicotine delivery capability (i.e., nicotine flux) among current combustible cigarette users.

We will compare abuse liability indices between three FDA authorized ECIG products that vary in nicotine flux (but are all tobacco flavor) and own brand cigarettes. We will also test the influence of ECIG flavor availability (tobacco vs. menthol) within three ECIG product classes.

We hypothesize that as nicotine flux is lowered, abuse liability indices will be lowered.

We also hypothesize that across ECIG product classes, abuse liability indices will be higher for menthol-flavored products.

3. * Describe the study's specific aims or goals. Use lay language whenever possible.

Aim 1: Compare the abuse liability of own brand (OB) cigarettes and three FDA-authorized tobacco flavor ECIGs that vary by nicotine flux.

Aim 2: Test the influence of ECIG flavor availability (tobacco vs. menthol) within each ECIG product class.

4. * Describe the scientific benefit or importance of the knowledge to be gained:

The benefits of this research are of a scientific nature. Specifically, we aim to use study results to inform our understanding of the abuse liability of ECIG liquid characteristics as well as provide information to guide the appropriate regulation of ECIGs.

In particular, the use of ECIGs has become increasingly popular, especially among individuals aged 18-24. New regulations are being targeted at this age group and need to be tested in this age group before implementation. The overarching theme of the Center for the Study of Tobacco Products is to provide regulators (FDA and others) with a suite of tools that allow them to test regulations before they are implemented to determine if those regulations will have

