1. May participate in any study interaction or intervention (Including screening, consenting, and study activities)

AND/OR

2. You obtain any data/specimens about (regardless of identifiability)

at VCU and at other sites under the VCU IRB's oversight. See the help text for additional guidance.

100

2. If this is a multi-Center Project, what is the maximum anticipated number of subjects across all sites?

N/A

3. * Provide justification for the sample size by explaining how you arrived at the expected number of participants and why this number is adequate for answering the research questions:

This study manipulates e-cigarette flavor and nicotine flux systematically, testing the hypothesis that abuse liability will be related directly to flux or flavor among a sample of cigarette smokers. Previous studies using this type of design are limited.

Thus, we calculated a sample size to achieve a power of >0.80 with $\alpha < 0.05$ and assuming a small effect size (Cohen's $f=0.20$) and moderate repeated measures correlation ($r=0.5$) in a repeated measures ANOVA with nicotine flux as within-subjects factors ($N=32$; GPower).

In this study, 36 cigarette users will attend the lab for 4 sessions: 1) own brand cigarette (always the first session), 2) NJOY Ace 2.4% nicotine ECIG (Menthol and Classic Tobacco flavor), 3) NJOY Ace 5.0% nicotine ECIG (Menthol and Classic Tobacco flavor), and 4) NJOY Daily ECIG 6% nicotine (Menthol and Extra Rich Tobacco).

We hypothesize that flux will be positively associated with willingness to pay (drug purchase task) and willingness to substitute e-cigarettes for own brand cigarettes (cross-product drug purchase task), and inversely to price sensitivity (drug purchase task) for all smokers.

We hypothesize that within class, menthol flavored products will be positively associated with willingness to pay (drug purchase task) and willingness to substitute e-cigarettes for own brand cigarettes (cross-product drug purchase task), and inversely to price sensitivity (drug purchase task) for all smokers.

It is possible that we would consent up to 100 participants in order to obtain 36 participants who complete the entire study.

4. * List the study inclusion criteria:

All participants must be healthy (determined by self-report), at least 18 years old (verified by photo ID), willing to provide informed consent, and attend the lab. Participants must agree to use designated products according to the study protocol.

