Participants who have already consented to participate in the CSTP registry may be contacted via phone or e-mail and told about this study. Individuals who are participants in other, ongoing CSTP studies (participants with whom we have a pre-existing relationship) may be verbally referred to this study and directed to either call the laboratory or visit the website indicated on the advertisements, if they are interested.

Participants who are eligible and who choose to enroll may be contacted via text for appointment reminders if they agree (see scripts).

6. * Does this study have a separate protocol document (i.e. a multisite or sponsor's protocol) that contains a detailed description of the study's methodology?

☐ Yes

☒ No

7. * Since a separate protocol document is not uploaded, describe the proposed research using language understandable to those IRB committee members whose expertise is not scientific. The description must include:

- 1. A statement explaining the study design**
- 2. A detailed description of all the procedures that will be followed to carry out the study, preferably in sequential order, and in sufficient detail that the study's methods could be replicated**
- 3. The schedule and frequency of when and how procedures will be conducted (e.g. in person, online, phone, paper, etc.)**
- 4. A description of all research measures/tests/interventions that will be used, including analyses/tests conducted on specimens/biological samples (if applicable)**

See the help text for additional guidance

Overview. This study involves 36 cigarette users who will complete 4, within-subject, laboratory sessions that differ by the product used: 1) own brand cigarette, 2) NJOY Ace 2.4% nicotine ECIG (Menthol and Classic Tobacco flavor), 3) NJOY Ace 5.0% nicotine ECIG (Menthol and Classic Tobacco flavor), and 4) NJOY Daily ECIG 6% nicotine (Menthol and Extra Rich Tobacco). The first condition for all subjects will be their own brand cigarette which is completed at the conclusion of the in-person screening session or scheduled immediately following (if the participant is unable to complete this condition at the in-person screening session). The subsequent three sessions will be assigned using a Latin-square following enrollment and within each session participants will sample and evaluate two flavors of each session's product (session flavor order is incorporated into the Latin-square condition order assignment).

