Procedure. Following the in-person screening procedure and confirmation of eligibility, participants will be asked to complete 4 sessions the first of which will begin immediately following the in-person screening (or a day/time that is more convenient for the participant). Subsequent sessions must be scheduled at least 48 hours apart. Participants are not required to abstain from nicotine/tobacco (as we are not testing the ability of these products to suppress abstinence related symptoms or measure acute self-administration behavior), food, or caffeine prior to any session.

Of note, research staff will use Zoom, as an intercom to communicate with participants whenever possible during sessions.

At the start of the session, participants will be asked about symptoms experienced since their last visit (with the exception of session 1, if completed at the in-person screening session; see Presession symptom Checklist). Answers given about respiratory and gastrointestinal symptoms will be compared to the participants' previous answers, and if any symptoms have become more frequent or more severe, the medical monitor and/or study nurse will be asked to review the symptoms. In some cases, we may contact [name] to determine if a session can proceed.

Next, participants will have their breath tested (expired carbon monoxide [CO]) and physiologic data collection will begin. We will check blood pressure once at the beginning of the session and again at the end. Heart rate will be measured continuously throughout the session. Immediately after session onset, participants will have a 30-minute rest period.

During rest periods, participants will not be allowed eat or drink outside beverages, but we will provide water to drink and they are invited to use their phone, read books/magazines, or watch movies that we provide to them.

After the 1st rest period, participants will complete subjective measures 1. Immediately after completing subjective measures 1, participants will sample the session-specific product (5 self-directed ECIG/own brand cigarette puffs over 10 minutes). After sampling is complete they will complete subjective measures 2. Ten minutes after their sampling has been completed, they will complete the DPT/CP-DPT. The DPT/CP-DPT takes approximately 10 to 15 minutes to complete. Please note at session 1, only the DPT will be completed, blood pressure will be checked, physio data collection will end, and then the session will end.

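### Own-brand cigarettes are always session 1, so the Aim 1 cigarette-versus-ECIG contrast is aliased with session order and should not be confirmatory or enter the flux test

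*Combined protocol and SAP*

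**What the plan says.** The aims in Background, Rationale and Goals, item 3, repeated in Study Procedures, item 2, make OB a comparator: "Aim 1: Compare the abuse liability of own brand (OB) cigarettes and three FDA-authorized tobacco flavor ECIGs that vary by nicotine flux".

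Its position is fixed. The sample-size justification (Study Population, item 3) lists "1) own brand cigarette (always the first session"). The overview in Study Procedures, item 7, says: "The first condition for all subjects will be their own brand cigarette which is completed at the conclusion of the in-person screening session". It adds an alternative, "or scheduled immediately following (if the participant is unable to complete this condition at the in-person screening session"), and the Procedure paragraph also allows session 1 on "or a day/time that is more convenient for the participant".

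Rotation applies only to the rest: "The subsequent three sessions will be assigned using a Latin-square following enrollment". Each ECIG session has two flavors, and "session flavor order is incorporated into the Latin-square condition order assignment".

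The content of session 1 differs too: "Please note at session 1, only the DPT will be completed". It has one product and is limited to 70 minutes. Sessions 2 to 4 have two products, each followed by the DPT and the cross-product task (CP-DPT), within 140 minutes.

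The Data analysis paragraph describes a mixed ANOVA in general terms, with regression or mixed linear models as alternatives and Tukey or Bonferroni-corrected contrasts. It names no session, period or within-session position term and does not say that OB is only a reference.

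**The concern.** In a within-subject comparison, rotation is what separates a product from the occasion on which it is tested. Here the ECIGs have that protection and OB does not. Anything particular to session 1 goes into the OB mean in full: it is the first test session, by default it follows a screening visit of about 1 to 1.5 hours, it has one product, and it is the lowest-paid session ($50, rising to $125 for session 4). A larger sample makes the biased estimate more precise but does not remove the bias.

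At stake is the OB-versus-ECIG statement in Aim 1, in a study intended to inform tobacco regulation. A second risk follows if OB is entered as a fourth level of the product factor: the overall F test can then be significant because of session 1 alone.

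**Working it through.** **Plan's own figure.** The sample-size paragraph gives N = 32 for f = 0.20, r = 0.5, alpha 0.05 and power above 0.80. The usual formula is λ = f²·N·m/(1 − r), with m − 1 and (N − 1)(m − 1) degrees of freedom and sphericity assumed. The N needed for 80% power is 42 with m = 3, 36 with m = 4 and 32 with m = 5. So 32 fits five measurements, while the planned 36 completers fit four conditions (λ = 0.04 × 36 × 4 / 0.5 = 11.52, power 0.81). That mismatch is a separate matter. Only N = 36 and r = 0.5 are carried forward.

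**Structure.** Let τ be product effects and π session effects.

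- Expected OB mean: μ + τ(OB) + π₁.
- Expected mean of ECIG k when rotated evenly over sessions 2 to 4: μ + τ(k) + (π₂ + π₃ + π₄)/3.
- OB minus ECIG k: [τ(OB) − τ(k)] + [π₁ − (π₂ + π₃ + π₄)/3]. The second bracket never cancels.
- ECIG k minus ECIG j: τ(k) − τ(j). The session effects cancel.

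The design matrix for 36 participants confirms this. It assumes all six ECIG orders and both flavor orders, because the square itself is not shown.

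| Fixed effects | Columns | Rank | OB vs ECIG estimable | ECIG vs ECIG estimable |
|---|---|---|---|---|
| participant + product | 39 | 39 | yes | yes |
| + session | 42 | 41 | no | yes |
| + session + position + flavor | 44 | 43 | no | yes |

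Replacing categorical session with a linear trend, extrapolated back to session 1, makes OB versus ECIG estimable, with its variance multiplied by about 1.5. The data cannot test that trend at session 1, because no ECIG is ever used there.

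**Size (illustration).** Assume no true OB–ECIG difference and a pure session-1 shift of g SD.

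- One pairwise contrast: the SD of a difference is √(2(1 − r)) = √(2 × 0.5) = 1, so the noncentrality is g√36 = 6g on 35 df.
- Four-level omnibus F with means (g, 0, 0, 0): f = g√3/4, with λ as above on 3 and 105 df. For g = 0.2, f = 0.087 and λ = 2.16.

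| Assumed shift g | Pairwise, unadjusted | Pairwise, Bonferroni for 3 | Omnibus F including OB |
|---|---|---|---|
| 0.1 SD | 9% | 4% | 8% |
| 0.2 SD | 21% | 11% | 20% |
| 0.3 SD | 42% | 25% | 41% |

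A session-1 shift of 0.2 × 4/√3 = 0.46 SD would by itself equal the planned f = 0.20 across four conditions.

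**The case against.** The case for the plan is substantial. The subjective measures, DPT and CP-DPT are all reviewed or practiced at screening, so session 1 is not the first contact with the tasks. Running OB directly after screening is the default, not the rule. Every session has the same 30-minute rest before the first sampling, so an ECIG sampled first in its session matches OB on the timeline within the session. The stated hypotheses concern flux and flavor; none predicts an OB–ECIG difference. The CP-DPT is not given in session 1, so it has no OB level. The rates above also assume no true difference, whereas the grant strategy reports earlier work in which smokers were generally willing to pay less for ECIGs than for their own brand. Bias in the estimate may therefore matter more than false rejection.

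All of this stands, and it limits the scope of the point. None of it removes the aliasing: practice may shrink a session-1 effect, and a separate day may remove the screening-visit element, but OB is still first for everyone.

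A reader might infer more than the documents support:

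- **Longer time since the last cigarette in session 1.** This is plausible but not documented. No abstinence is required before any session, and the text does not say whether smoking is allowed between screening and session 1.
- **A false flux claim.** No text says that an omnibus F including OB will be read as evidence on flux. The plan is only silent on whether OB enters that test.
- **Higher error rates.** OB against the mean of the three ECIGs gives 30% at 0.2 SD and 57% at 0.3 SD (SD of the contrast √(0.5 × 4/3) = 0.816), but the plan names no such contrast.

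**Conclusion.** The point holds for one comparison: OB versus ECIG on DPT and subjective outcomes. It is aliased with session order and session-1 conditions, and the Data analysis paragraph neither handles this nor acknowledges it. The aliasing follows from the stated design and needs no numerical assumption. Its effect on the result does: neither the size nor the direction of a session-1 shift can be taken from the documents, so the rates are illustrations for 0.1 to 0.3 SD.

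Flux contrasts among the ECIGs and Aim 2 stay estimable, provided the Latin square balances session and flavor order as described. It would be wrong to read this as a failure of the trial's main hypotheses, or as proof that OB must be rotated.

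**What to change.** Amend the Data analysis paragraph as follows.

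1. Run the confirmatory flux test on the three rotated tobacco-flavor ECIGs only, with session and within-session position in the model. Keep OB out of that test.
2. Report OB versus each ECIG as a benchmark estimate with its interval, state that it is confounded with session order and session-1 conditions, and do not present it as confirmatory.
3. Add two sensitivity analyses: OB against ECIGs sampled first in their session, and a split by whether OB was done on the screening day. The first reduces within-session differences. The second addresses the screening visit, but the split is not randomized. Neither removes the order effect.

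This needs no new data. The cost is a weaker OB-versus-ECIG claim. It also makes plain that the flux test has three levels, for which 36 completers give 73% power at f = 0.20 and r = 0.5 (42 are needed for 80%); the sample-size paragraph should say so.

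Rotating OB into a four-session square is a trade-off and is not required. Four sequences by two flavor orders make 8 cells, and 36/8 = 4.5 does not balance. The present layout can balance if all orders are used (6 × 2 = 12 cells, 36/12 = 3). OB would still be a one-product, DPT-only session, and most participants would lose the same-day visit.

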Participants. A total of 36 adults (age 18+) who currently use cigarettes will be enrolled. We will attempt to recruit an equal number of menthol and non-menthol preferring smokers as well as men and women of diverse racial/ethnic backgrounds, although this study is not intended to address gender or race/ethnic differences.

Recruitment and Enrollment. Participants will first be screened via phone or online, via a multi-study screening process/registry described in HM20002567 (see attachment "Registry consent form and questions"). Participants are automatically screened for all ongoing CSTP studies, but participants can tell study staff if they are interested in screening for a particular study only, and study staff will make a note of this preference.

Once initial screening is completed (either over the phone or via the internet), potentially eligible participants will be invited to the lab to complete in-person informed consent, additional screening, and familiarization with study procedures (approximately 1 hr, \$15/hour compensation). Once participants have been seated in a private study room, research staff will communicate with the participants primarily using Zoom as an intercom, to speak/interact with participants. Prior to in-person data collection, staff will review the informed consent in person and/or using a Powerpoint/video tool to ensure they understand the study, its risks and benefits, and their rights as research participants. Participants will have the opportunity to ask questions to the research staff, prior to signing the consent document. Following documentation of informed consent, participants will complete baseline measures to confirm eligibility, have their blood pressure and heart rate checked, provide a urine sample that will be tested for cotinine level

(to confirm current smoking status) and pregnancy (women only), and provide a exhaled breath carbon monoxide (eCO) sample. Age will be verified by asking participants to provide some form of identification that includes a date of birth. All study procedures (including subjectives, Drug Purchase Task, Cross-Product Drug Purchase Task) will be reviewed/practiced using approved measures and/or Powerpoint/video-based tools. Participants also will complete the Minute Discounting Task.

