Individuals whose blood pressure levels are elevated (≥ 140 mmHg systolic or ≥ 90 mmHg diastolic) during screening or at a session will be provided with a blood pressure information sheet by the research staff (see study document). This sheet will be provided at the first instance of elevated blood pressure observed during the study.

Participants who report illegal drug use at baseline or self-disclose at a later point in the study (other than marijuana/cannabis) will be provided a copy of the Substance Use Resource Handout. Participants are not required to take the handout.

Participants will be asked during the baseline questionnaire whether they would like to receive a brief summary of study findings when the study is completed and if yes preferred contact information (for disbursement of this summary). This information will be completed once the brief study summary is disbursed.

New recruits will replace participants who do not complete the study. Accrual ends when the required number of completers is reached.

Products. Own brand tobacco cigarettes and alternative tobacco products will be purchased locally and/or online by VCU approved staff. If own brand cigarettes are not available at the in-person screening session (due to supply-chain or other access issues), participants will be asked to provide one of their own products and receive compensation for use during that session (\$5 for one cigarette). Alternative tobacco products tested will be 1) NJOY Ace 2.4% nicotine ECIG (Menthol and Classic Tobacco flavor), 2) NJOY Ace 5.0% nicotine ECIG (Menthol and Classic Tobacco flavor), and 3) NJOY Daily ECIG 6% nicotine (Menthol and Extra Rich Tobacco).

Of note in terms of regulatory status for the ECIG products tested. Products in Classic Tobacco flavor and Extra Rich Tobacco are currently FDA authorized for marketing/sale in the US (as of 1.24.2023). Products in Menthol flavor are still under FDA review for authorization and have not been denied for marketing/sale and thus are still legal for use for those appropriate age (as of 1.24.2023).

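### The Latin-square assignment of sessions 2 to 4 is not spelled out; listing and using all six product orders would balance the preceding product within the planned 36 completers

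*Combined protocol and SAP*

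**What the plan says.** All references are to the Combined protocol and SAP. Study Procedures, question 7 (Overview), fixes session 1: "The first condition for all subjects will be their own brand cigarette". For the three e-cigarette products it says: "The subsequent three sessions will be assigned using a Latin-square following enrollment". Two flavors are sampled in each of these sessions, and "session flavor order is incorporated into the Latin-square condition order assignment".

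The sequences, the number of squares and the layout of flavor order are not given. Question 6 states that there is no separate protocol document, so the scheme is not described elsewhere.

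Other relevant statements:

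- Procedure: "Subsequent sessions must be scheduled at least 48 hours apart".
- Participants: "We will attempt to recruit an equal number of menthol and non-menthol preferring smokers".
- Recruitment and Enrollment: "New recruits will replace participants who do not complete the study". Whether a replacement takes over the vacated sequence is not said.
- Study Population, question 3: the study may "consent up to 100 participants in order to obtain 36 participants who complete the entire study".
- Data analysis: regression, ANOVA or mixed linear models may be used. No term for session position, sequence or previous product is named.

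**The concern.** With three products, one Latin square puts each product equally often in each session position but always in the same cyclic order. In ABC, BCA, CAB, product B is only ever preceded by A, C by B, and A by C. Any influence of the previous product is then tied to the product being judged.

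The 48-hour gap deals with residual nicotine. It does not obviously deal with remembered comparison, such as valuing a weaker e-cigarette in a hypothetical purchase task after a stronger one. The flux hypothesis is about an ordered gradient, so a distortion that differs between its two steps would change the apparent shape of the result. With only one square, a model that adjusts for the previous product would be too imprecise to settle the question.

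**Working it through.** The plan gives no figure for order balance, so there is none to reproduce.

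**Inputs.** Three e-cigarette products A, B, C in sessions 2 to 4 (Overview) and 36 completers (Study Population, question 3). I take one outcome value per participant and session, as in the tobacco-flavor comparison of Aim 1. Session 2 follows own brand for everyone, so any own-brand carry-over common to the three products goes into the session effect. L_A, L_B, L_C denote what each product adds to the next session. The documents give no values for them.

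**1. Counts.** Only two sets of three orders form a 3 x 3 Latin square: {ABC, BCA, CAB} and {ACB, BAC, CBA}. Together they are the six possible orders.

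| Design, N = 36 | Each product in each position | Ordered transitions |
|---|---|---|
| One square x 12 | 12 | three occur 24 times, their reverses 0 times |
| Six orders x 6 | 12 | all six occur 12 times |

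**2. Bias without a carry-over term** (model: participant, session, product). Positions are balanced, so the contrast is a difference of product means.

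- First square: B follows A in 24/36 = 2/3 of participants, and A follows C in 2/3. Bias of B - A = (2/3)(L_A - L_C). Likewise C - B: (2/3)(L_B - L_A); C - A: (2/3)(L_B - L_C).
- Second square: B - A: (2/3)(L_C - L_B); C - B: (2/3)(L_A - L_C); C - A: (2/3)(L_A - L_B).
- Six orders: each product follows each other product in 12/36 = 1/3. Bias of B - A = (1/3)(L_A + L_C) - (1/3)(L_B + L_C) = (1/3)(L_A - L_B). Likewise C - B: (1/3)(L_B - L_C); C - A: (1/3)(L_A - L_C).

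The coefficients fall from 0.67 to 0.33.

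**3. Illustration (assumed, not from the documents).** Let A, B, C be low, middle and high flux. Suppose the low product raises the next rating by d, the high product lowers it by d, and the middle one does nothing: L = (d, 0, -d).

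| Contrast | First square | Second square | Six orders |
|---|---|---|---|
| B - A | +1.33d | -0.67d | +0.33d |
| C - B | -0.67d | +1.33d | +0.33d |
| C - A | +0.67d | +0.67d | +0.67d |

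With one square, the two steps of the gradient are distorted in opposite directions, and which way depends on the square chosen. With six orders both steps shift equally. The lowest-versus-highest bias is the same in all three designs.

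**4. Variance of a pairwise contrast** (least squares, N = 36; sigma^2 is the within-participant residual variance).

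| Model | One square | Six orders |
|---|---|---|
| No carry-over term | 2/36 = 0.0556 sigma^2 | 0.0556 sigma^2 |
| Previous product fitted | 0.278 sigma^2 | 0.0694 sigma^2 |

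With the previous product fitted, the ratio is 0.278/0.0694 = 4, so one square has twice the standard error. Relative to the unadjusted contrast, the adjustment multiplies variance by 0.278/0.0556 = 5 with one square and by 0.0694/0.0556 = 1.25 with six orders.

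**5. Fit to the design.** 36/6 = 6 per order. With two mirrored flavor-order patterns, 6 x 2 = 12 sequences and 36/12 = 3 each. Freely varied flavor order needs 6 x 2^3 = 48 sequences, more than 36. If the menthol-preference groups reach 18 each, six orders fit (18/6 = 3) but twelve sequences do not (18/12 = 1.5).

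**The case against.** A reader might infer that the trial uses a single 3 x 3 square and that its flux contrasts are therefore confounded with the preceding product. The documents do not show this. Flavor order is built into the assignment, so the list is more than a bare three-row square. The move from a calculated 32 to 36 completers is also suggestive: three sequences would need only 33, whereas 36 suits six or twelve. That is inference only, since six sequences could equally be three product orders with two flavor patterns. This objection stands: what is established is an unspecified scheme, not an imbalance.

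A second tempting reading is that six orders remove carry-over bias. They do not. In the illustration the C - A bias is unchanged. If only C carries over (L = 0, 0, 1), the second square gives a C - A bias of 0 and six orders give -0.33, so a particular contrast can do worse.

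Third, the fourfold variance difference applies only to a model with a previous-product term, which the plan does not name. For the unadjusted contrast the designs are equally precise.

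Fourth, general practice effects depend on session position, which one square already balances. The tasks are also rehearsed at screening, and the purchase task is completed once for own brand. That leaves contrast with the previous product, whose size is undocumented.

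These objections limit the claim but do not remove the case for six orders. Every transition would be observed, the coefficients would be smaller, and a carry-over check would be informative, all at the same N.

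**Conclusion.** This is a minor but worthwhile design improvement. The protocol should state its sequences. If they come from one 3 x 3 square, all six orders are better: each transition occurs 12 times instead of 24 or 0, carry-over coefficients in unadjusted pairwise contrasts fall from 0.67 to 0.33, and the previous-product check has contrast variance 0.069 rather than 0.278 sigma^2.

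These figures assume 36 completers spread evenly over the sequences, one value per session, and additive carry-over from the immediately preceding product only. The practical consequence for this trial cannot be sized, because no magnitude of carry-over is given. The conclusion does not extend to a claim that the planned flux contrasts are biased, or that six orders would make them unbiased. The own-brand session, always first, remains confounded with session position under any ordering of sessions 2 to 4. If both squares are already used, only a sentence of clarification is needed.

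**What to change.** - List the sequences in the Overview, including flavor order. Use all six product orders for sessions 2 to 4, six completers each. With two mirrored flavor-order patterns this gives 12 sequences with three completers each.
- If balance within menthol-preference groups is wanted, balance the six product orders there (three per order in groups of 18). Split the flavor patterns 2:1 in one group and 1:2 in the other for each order, which still gives 2 + 1 = 3 per sequence overall.
- Assign each replacement the sequence of the participant replaced, so that balance holds among completers.
- In Data analysis, include session number in the model for sessions 2 to 4, and add previous product as a sensitivity check. Own brand cannot share a free session term, because it occurs only in session 1.

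The cost is a different assignment list and a few lines of text, with no added participants, visits or measures. The sensitivity check carries 25% more contrast variance than the unadjusted model (0.0694 versus 0.0556 sigma^2), which is a reason to keep it as a check and not as the main analysis.
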